We will conduct a randomized comparative effectiveness trial of peer-facilitated, online, 6-week group MI vs. MI with a trauma-informed SGM affirmative care approach. Randomization will be counterbalanced by treatment status: treatment naive versus treatment-experienced (prior treatment not within the past 60 days). Randomization will be based on a list of computer-generated random numbers. We will randomize 356 SGM male trauma survivors to either condition. Assessments will occur at baseline, post-intervention, and at 60- and 120-day follow-ups, from the end of the intervention.

Comparators. Traditional MI will be compared to MI with trauma-informed SGM affirmative care (MI+). Groups will take place 1.5 hours once a week for 6-weeks and will be led by two peer specialists trained in MI or tailored MI. Groups will consist of approximately 8-10 members and be closed for the duration of the group. It is anticipated that new groups will begin every other month (allowing for a two week break between groups) to reduce burden on peer specialists and supervisors.

Traditional MI groups. Six traditional MI groups will take place for 1.5 hours online facilitated by two peer specialists.

Trauma-informed, SGM+ affirmative care MI groups. Six tailored MI groups will take place for 1.5 hours online facilitated by two peer specialists. Please see Appendix A for a detailed overview and outline of the major supplemental MI modules aimed at SGM minority stress, traditional masculinity, and male sexual abuse.

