Through workshops and ongoing supervision/consultation, we will train peer leaders to competently deliver both versions of MI and conduct a randomized controlled trial comparing the two versions of MI to enhance treatment engagement in SGM male survivors with mental health problems. All SGM male survivors who meet inclusion criteria, including significant emotional distress, will complete pre-test measures and be randomized to 6-week traditional MI delivered by peers in online groups or 6-week MI with trauma-informed, SGM affirmative care delivered by peers in online groups. Randomization will be counterbalanced by treatment status: treatment naive versus treatment-experienced (prior treatment but not within the past 60 days). This same procedure of counterbalancing by treatment status was previously used in the randomized controlled trial of MI (Burke et al., 2003) to help Iraq and Afghanistan veterans with mental health difficulties engage in more mental health services. Participants will complete pre-intervention (baseline), end of the 6-week intervention, 60- and 120-days follow-up assessments via an online survey platform, to determine if there was an increase in formal mental health treatment engagement, and any significant changes in mental health symptomology (i.e., PTSD, depression, high-risk drinking, and

illicit substance use). Peer leaders will co-facilitate groups throughout the study. It is anticipated that a peer leader will run between 1-3 groups throughout the study.

Parent Study Screening and Participant Eligibility Criteria.

Once recruitment advertisements are posted on the various websites (listed in detail below), those interested in finding out more information, will be directed to a website that contains the informed consent and Frequently Asked Questions about participation. Participants will then be asked to complete a short questionnaire including demographic questions with their contact information to be sent to a member of the research team to set up a screening appointment via telephone with the interested participant.

Screening

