Those participants who meet inclusion criteria will be provided a link to the online surveys for baseline assessment. Measures will include prior and current mental health treatment engagement, barriers and beliefs around seeking formal mental health treatment, as well as measures assessing symptomatology (e.g., substance use, depression, PTSD). At the completion of the 6-week group, participants will complete post-intervention assessments and 60- and 120-day follow-up assessments on the various outcome measures. A summary of the timing and purpose of assessments is shown in Table 1.

Baseline, Post-Intervention and Follow-up Outcomes

Primary Outcome: Mental Health Treatment Engagement. The primary outcome here will be the binary distinction between those who initiated mental health treatment/reinitiated mental health treatment versus those who did not. Mental health treatment engagement will be operationally defined as having ≥ 1 visit(s) or scheduled appointments to any mental health services within 120 days of the last online group.

Primary Outcome: Depression. Center for Epidemiological Studies Depression Scale (CES-D; Radloff, 1977) is a 20-item questionnaire that asks about experience and frequency of depressive symptoms over the past week. A score of 16 or higher identifies those individuals who are at risk for major depression.

Secondary Outcome(s): will include PTSD, alcohol and drug abuse, quality of life, and service utilization.

PTSD Checklist for DSM-5 (PCL-5; Weathers et al., 2013) is a 20-item instrument that corresponds to the current psychiatric diagnostic criteria for PTSD.

Alcohol, Smoking and Substance Involvement Screening Test (ASSIST; WHO ASSIST Working Group, 2002; Humeniuk et al., 2008) is an 8-item measure of participants’ use of alcohol, tobacco products, and other drugs across their lifetime and in the past three months.

Inventory of Psychosocial Functioning (IPF-B; Rodriguez, Holowka, & Marx, 2012) is a brief 7-item scale that assesses functional impairment or quality of life related to trauma and PTSD.

The Service Use and Resource Form (SURF; Rosenheck et al., 2016) is a questionnaire assessing current living situation, use of inpatient and outpatient mental health and alcohol or drug treatments, psychotropic medication use, and use of other support services. The SURF will be administered during screening, baseline, post-intervention and follow-up.

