Fidelity monitoring will occur ad hoc by independent raters using audio-recordings of intervention sessions. At least 30% of the sessions (traditional MI and trauma-informed MI) will be coded ($n = 90$). Three coders will rate each session. [name] will host a training with the raters to familiarize them with the rating scales and interventions. The three raters will conduct the fidelity ratings over a six to eight month period (approximately) between June 2021 and February 2022. The three raters ([name], [name] and [name]) have previous experience conducting this task and will be supervised by [name]. Audio recordings of selected group sessions will be sent to the raters using Yale's secure file transfer (FileLocker).

Assessment Measures. Peer specialists will also be asked to complete a reflective journaling exercise (see attached) after each treatment cycle they co-facilitate. In addition, they will complete several assessments measures (see attached) prior to their attendance at the MI training then again after they attend the MI training. Peer specialists will be asked to answer approximately three open-ended questions at the end of the study.

Table 1: Assessment Schedule

Assessment Name		Screening	Baseline	Post-intervention	60-Day Follow-up	120-Day Follow-up
Peer Specialists	Independent Tape Rater Scale			x		
Male Survivors	Demographic and SGM identification	x	x	x	x	x
	Sexual abuse characteristics	x				
	Life Events Checklist	x				
	Mini International Neuropsychiatric Interview	x				
	Telephone-Assessed Mental State (TAMS)	x				
	Columbia-Suicide Severity Rating Scale (C-SSRS)	x	x	x	x	x

Brief Dissociative Experiences Scale (DES-B Modified for DSM-5)		x	x	x	x
Center for Epidemiological Studies-Depression Scale	x	x	x	x	x
PTSD Checklist for DSM-5		x	x	x	x
Alcohol Smoking and Substance Involvement Screening Test (ASSIST)		x	x	x	x
Inventory of Psychosocial Functioning		x	x	x	x
Barriers to Help Seeking Scale		x	x	x	x
Conformity to Masculine Norms Inventory		x	x	x	x
Minority Stress Scale		x	x	x	x
Working Alliance Inventory			x		
Service Use and Resource Form (SURF)	x	x	x	x	x
Adult Resilience Measure – Revised (ARM-R)		x	x	x	x

Participant Population: Provide a detailed description of the types of participants who will be recruited into this study.

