Webber, K. H., Tate, D. F., Quintiliani, L. M. (2008). Motivational interviewing in internet groups: a pilot

study for weight loss. *J Am Diet Assoc*, 108(6),1029-32.

West, D. H., Harvey, J. R., Kruckowski, R. A., Prewitt, T. E., Priest, J., & Ashikaga, T. (2016). Do individual online motivational interviewing chat sessions enhance weight loss in a group online weight control program? *Obesity*, 24(11), 2234-2340.

Westra, H. A., Aviram, A., & Doell, F. K. (2011). Extending motivational interviewing to the treatment of major mental health problems: Current directions and evidence. *Canadian Journal of Psychiatry*, 56(11): 643-650. Doi: 10.1177/070674371105601102

WHO ASSIST Working Group. (2002). The Alcohol, Smoking and Substance Involvement Screening Test (ASSIST): development, reliability and feasibility. *Addiction*, 97(9), 1183-1194.

Williams, J. K., Kisler, K. A., Glover, D., & Sciolla, A. (2011). *Exploring childhood sexual experiences and vulnerability to intimate partner violence among African American MSMW: Was that abuse or love?* New York: Nova Science Publishers.

Analysis Plan

To assess the success of randomization, baseline demographic and clinical characteristics, the two randomized groups were compared using chi-square tests for categorical variables and t-tests or Mann-Whitney tests for continuous variables. Data analyses were conducted on the intent-to-treat sample. All variables were evaluated for their distributional properties and data processing errors. Robust estimators were used to address non-normal data.

Variables were assessed for amount and pattern of missing data. Full information maximum likelihood estimation was used in subsequent analyses to address missingness. Inclusion of informative variables were included as needed. Analyses were conducted in SPSS 28.0 (IBM, 2021). For outcome analyses, linear mixed models (LMM) of mental health symptoms were modeled as a repeated measures outcome variable, nested within participants. Baseline demographic, clinical variables, and sexual abuse experiences were included as time-invariant covariates (between participants), as was treatment group. Thus, for each outcome, the primary analysis included all observations nested in persons and cohorts, controlling for baseline clinical and demographic variables.

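### At the post-intervention visit roughly half of the ASSIST's three-month recall window precedes the first group session, so a substance-use effect pooled over visits is pulled toward zero

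*Combined protocol and SAP*

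**What the plan says.** The outcomes part of the Research Plan (Section IV, item 3) says that the secondary outcomes "will include PTSD, alcohol and drug abuse, quality of life, and service utilization". The ASSIST is the instrument for alcohol and drugs, and it records use "across their lifetime and in the past three months". Table 1 (Assessment Schedule) marks it at baseline, post-intervention, 60 days and 120 days.

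On timing, the same item states "Groups will take place 1.5 hours once a week for 6-weeks" and "At the completion of the 6-week group, participants will complete post-intervention assessments". It also states "Assessments will occur at baseline, post-intervention, and at 60- and 120-day follow-ups, from the end of the intervention". No visit window is given for any of these assessments.

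The Research Plan says the repeated surveys are meant to detect "any significant changes in mental health symptomology (i.e., PTSD, depression, high-risk drinking, and" illicit substance use. Substance use is therefore among the symptoms that the Analysis Plan covers when it says "linear mixed models (LMM) of mental health symptoms were modeled as a repeated measures outcome variable, nested within participants". That section adds that the primary analysis of each outcome uses all observations. It does not say which ASSIST items or score are analysed, whether the reported treatment effect is visit-specific or averaged over visits, or how a recall period longer than the intervention is handled.

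**The concern.** A three-month recall question asked six weeks after the groups began covers a stretch of time in which no participant had yet received either intervention. Both arms should look alike over that stretch, so any difference in current use is mixed with a period of no difference. The mixed model would still treat the score as an ordinary post-treatment value.

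Two misreadings could follow. A null substance-use result at post-intervention could be taken as no early effect. A between-arm difference that grows from post-intervention to 60 days could be taken as delayed benefit, when part of the growth comes only from pre-intervention days leaving the window. If the three post-baseline visits are averaged, the summary effect inherits the dilution. The CES-D does not share the problem, because its one-week recall falls inside the intervention period.

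**Working it through.** The documents give no figure of their own on this point, so there is nothing to reproduce first.

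**Inputs**
- Recall window W: three months (Research Plan), taken here as 90, 91 or 92 days because the documents do not give days.
- Day t of the post-intervention survey, counted from the first session: day 42 for a nominal six-week group; day 35 if the survey is completed at the sixth weekly session, since five weekly intervals separate sessions 1 and 6. Delays after day 42 are shown because no visit window is stated.
- Follow-ups: 60 and 120 days from the end of the intervention.

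**Step 1. Share of the window before the first session** = (W - t)/W. The share after it is t/W.

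| Survey completed | Days before session 1 (W = 90 to 92) | Share before | Share after |
|---|---|---|---|
| Day 35 | 55-57 | 61-62% | 38-39% |
| Day 42 | 48-50 | 53-54% | 46-47% |
| Day 45 (3-day delay) | 45-47 | 50-51% | 49-50% |
| Day 46 (4-day delay) | 44-46 | 49-50% | 50-51% |
| Day 49 (7-day delay) | 41-43 | 46-47% | 53-54% |
| Day 56 (14-day delay) | 34-36 | 38-39% | 61-62% |

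At W = 91 and t = 42, the share before is 49/91 = 54% and the share after is 42/91 = 46%.

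**Step 2. The later visits (W = 91, groups ending on day 42)**
- 60-day visit: 42 + 60 = day 102. The window opens on day 102 - 91 = 11, so none of it precedes session 1, but 42 - 11 = 31 of 91 days (34%) fall while the groups are running.
- 120-day visit: 42 + 120 = day 162. The window opens on day 162 - 91 = 71, wholly after the groups end.

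**Step 3. Illustrative dilution.** This step assumes that the score weights every day of the window equally and that the full effect is present from session 1. The visible fraction at post-intervention is then t/W: 35/92 = 38% at the low end, 42/91 = 46% at day 42, and 49/90 = 54% at the high end. If instead the effect builds linearly from zero to full over 42 days, the visible fraction at day 42 is (42/2)/91 = 21/91 = 23%.

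**Step 4. Illustrative effect on a pooled result.** With the Step 3 assumptions, equal weights for the three post-baseline visits and a full effect at 60 and 120 days, the average keeps (0.46 + 1 + 1)/3 = 82% of the effect. The range is (0.38 + 2)/3 = 79% to (0.54 + 2)/3 = 85%.

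**The case against.** The strongest reply is that the comparison remains a valid randomised one. Both arms answer the same question over the same window, so past-three-month use at the end of the groups is a clearly defined quantity that is simply less sensitive to change. Only one of three post-baseline visits of one secondary outcome is involved, and if visit-specific contrasts are reported, the later visits are untouched. All of this stands, and it limits the point to sensitivity and interpretation. It does not remove the point, because the Analysis Plan neither commits to visit-specific contrasts nor mentions the overlap.

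A reader might infer four stronger things that the documents do not support:

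- **That more than half of the window is certain to precede the intervention.** This holds on day 35 or day 42. A delay of three to four days brings the share to about half, and seven days brings it below half.
- **That at most 46% of a true effect could be seen at that visit.** This needs a score that averages use evenly over the window. The documents give no ASSIST scoring or response categories. Coarse frequency categories, or recall weighted to recent weeks, could move the visible share either way.
- **That the lifetime items make the outcome unresponsive.** Nothing says these items enter the analysed score. If they did, a component that stays fixed after baseline would be balanced by randomisation. It would add spread between participants without shrinking the raw difference between arms.
- **That the 60-day visit is free of the problem.** Its window lies wholly after the first session, but about a third of it falls during the groups, so an effect that builds gradually would be somewhat diluted there too.

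The Analysis Plan is written in the past tense. Setting a collected visit aside now could look like a post hoc choice of time points, and the fix has to allow for that.

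**Conclusion.** The concern holds as a minor one. The calendar overlap follows directly from the stated recall period and visit schedule: roughly half of the ASSIST window at the post-intervention visit precedes the first session, with 46-62% covering completion from day 35 to day 49. Because that score enters the mixed model without qualification, any pooled substance-use contrast is pulled toward no difference. The direction does not favour either arm.

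The amount of dilution is not established. The 38-54% visible at that visit, and the 79-85% retained in a simple three-visit average, rest on even weighting over the window and an immediate full effect, neither of which the documents state. The trial can still estimate a substance-use effect from the later visits. Both primary outcomes are unaffected: treatment engagement is counted up to 120 days after the last group, and the CES-D asks about the past week.

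**What to change.** State in the Analysis Plan that, for the ASSIST:

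1. The analysed score uses the past-three-month items, with the scoring written out.
2. Treatment contrasts are estimated separately at each visit from the mixed model.
3. The main results are the 120-day contrast (window wholly after the intervention) and the 60-day contrast (window wholly after the first session, with about 31 of 91 days during the groups, to be stated alongside it).
4. The post-intervention contrast is reported separately with a note on recall overlap and is not pooled into an averaged effect.

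If the analyses have already been done, present this as a labelled sensitivity analysis beside the original model, so that no collected visit is dropped after the fact.

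No new data are needed. The cost is a few lines of analysis-plan text and one fewer time point in the main contrast for one secondary outcome.

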The ***Telephone-Assessed Mental State (TAMS; Lanska et al., 1993)*** is a brief, easily administered, easily scored cognitive assessment tool which can be administered by telephone. The TAMS uses 4 items from the extensively used Mini-Mental State Examination (MMSE) to assess for orientation to time and place, attention, and memory. In the population sample of Alzheimer's disease patients, TAMS scores correlated strongly with those of instruments administered face to face, including the MMSE.

The ***Service Use and Resource Form (SURF; Rosenheck et al., 2016)*** is a questionnaire assessing current living situation, use of inpatient and outpatient mental health and alcohol or drug treatments, psychotropic medication use, and use of other support services. The SURF will be administered during

screening, baseline, post-intervention and follow-up. This measure takes approximately 10-15 minutes to complete.

The ***Columbia-Suicide Severity Rating Scale (C-SSRS; Posner et al., 2011)*** is a widely used measure of suicidality that has been successfully implemented across many settings (e.g., military, primary care, etc.). It has demonstrated good convergent and divergent validity with other multi-informant suicidal ideation and behavior scales and has high sensitivity and specificity for suicidal behavior classifications. It is also sensitive to change over time. The C-SSRS is available in several versions free of charge, including a brief 6-item screener which can be used as a self-report or interview measure. The C-SSRS screener will be administered during the phone screening interview and at baseline, post-intervention and follow-up assessments. Any participants endorsing “high-risk” responses (i.e. those coded in red) will be flagged, and Drs. [name], [name], or [name] will conduct a follow-up phone assessment to determine their suicide risk and make a final eligibility determination.

Outcomes

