The ***Columbia-Suicide Severity Rating Scale (C-SSRS; Posner et al., 2011)*** is a widely used measure of suicidality that has been successfully implemented across many settings (e.g., military, primary care, etc.). The C-SSRS is available in several versions free of charge, including a brief 6-item screener which can be used as a self-report or interview measure. The C-SSRS screener will be administered during the phone screening interview and at baseline, post-intervention and follow-up assessments. Any participants endorsing “high-risk” responses (i.e. those coded in red) will be flagged, and Drs. [name], [name], or [name] will conduct a follow-up phone assessment to determine their suicide risk and make a final eligibility determination.

The ***Brief Dissociative Experiences Scale (DES-B Modified; Dalenberg & Carlson, 2010)*** is a brief 8-item self-report measure that assesses the severity of dissociative experiences in individuals aged 18 and older. Higher scores indicate a greater severity of dissociative experiences. As the DES-B can track changes in the severity of brief dissociative experiences over time, participants will be asked to complete the measure at baseline, post-intervention, and follow-up assessments.

Potential Moderators:

Barriers to Help Seeking Scale (BHSS; Mansfield, Addis, & Courtenay, 2005) is a 31-item scale measures several barriers to help-seeking (e.g., need for control and self-reliance, minimizing problem and resignation, concrete barriers and distrust of caregivers, privacy, and emotional control).

Conformity to Masculine Norms Inventory (CMNI-46; Parent & Moradi, 2009) assesses conformity to the following masculine norms: winning, emotional control, primacy of work, risk-taking, violence, heterosexual self-presentation, sexual activity, self-reliance, and power over women.

Minority Stress Scale (MSS; Norcini Pala et al., 2017) is a 43-item questionnaire that assesses individuals’ experiences of stigmatization, discrimination, and internalized homophobia due to their sexual orientation.

Working Alliance Inventory (WAI; Horvath & Greenberg, 1989), is a well-established measure of the therapeutic relationship. The measure contains three subscales (i.e., agreement on the goals of therapy, agreement on the tasks of therapy, and bond between client and therapist).

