Peer specialists will also be asked to provide consent for participation in a research study (see attached form). They will also be asked to complete an attestation form (see attached) to ensure they agree to all requirements/commitments required to serve as a peer specialist (see attached). Information will be collected on peer specialists (e.g. demographic information such as age, race/ethnicity, education level, etc.). In addition, peer specialists will be asked to complete assessment measures (as documented above) and a reflective journaling exercise to capture their experiences leading the groups (see attached).

If a participant informs the study staff that they are no longer able to participate in the group intervention (e.g. participant was randomized and then unable to complete all six online group sessions) the study staff will contact that participant to confirm receipt of their message and also note their eligibility to complete ongoing assessment measures (see example of outreach language with submission). Similarly, if a participant stops attending group, without explicitly informing the study staff of their inability to complete the six sessions we will contact them informing them they are still eligible to complete the follow-up assessment measures. If a participant withdraws from the study entirely, we will not contact them to gather additional data.

Participants who engage in the online groups will be offered the opportunity to share their e-mail address with their fellow group participants and the two peer leaders for their group. Participants will be informed by the peer leaders during the 6th session that they will be provided a link to a consent form that will allow them to choose if they would like to share their e-mail address with fellow group members and/or peer leaders. They will be informed both during the 6th session (by the peer leaders) and in the online consent form (sent by the study staff) that sharing their information is completely voluntary. We will require that each participant provide written consent indicating 1) their preferred name to share, 2) their e-mail address, and 3) to whom they provide permission to share their information with (see attached form). If a participant does not provide signed consent, or complete the form in its entirety, their information will not be shared.

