Peer leaders will be trained during a 3-day in-person meeting specifically on identifying and managing emotional distress. They will also get ongoing training during weekly supervision where supervising psychologists will check in weekly with peer specialists about any distress observed or noted in their group(s). Peer leaders will be required to alert the study PI via phone and e-mail within 30 minutes of the conclusion of the session when the participant expressed, or the peer specialist identified, emotional distress. The PI will directly contact the participant via phone to assess current risk and needs. When appropriate, the PI will provide area specific resources to the participant based on their location. The PI will utilize databases such as the clinician directory of the American Psychological Association and the International Society for Traumatic Stress Studies to make a local referral for the patient. In addition, the PI will provide the patient with information to the nearest emergency room, based on the participants stated location.

3. **Data and Safety Monitoring Plan:** Include an appropriate Data and Safety Monitoring Plan (DSMP) based on the investigator’s risk assessment stated below. (Note: the HSC will make the final determination of the risk to subjects.).

a. What is your assessment of the overall risk level for subjects participating in this study?

More than minimal risk.

b. If children are involved, what is your assessment of the overall risk level for the children participating in this study? Not applicable.

c. **Include an appropriate Data and Safety Monitoring Plan. Examples of DSMPs are available here <http://your.yale.edu/policies-procedures/other/data-and-safety-monitoring-plan-template>** for

i.	Minimal risk
ii.	Greater than minimal/moderate risk

1. Personnel responsible for the safety review and its frequency:

The PI will be responsible for monitoring the data, assuring protocol compliance, and conducting the safety reviews at the specified frequency, which must be conducted at a minimum of every 6 months (including when re-approval of the protocol is sought). During the review process, the PI (monitor) will evaluate whether the study should continue unchanged, require modification/amendment, or close to

enrollment. Either the PI or the IRB have the authority to stop or suspend the study or require modifications.

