Peer leaders will receive \$180.00 for each group they co-facilitate. Specifically, they will receive \$60.00 at the end of the third group session and another \$60.00 at the end of the sixth group session they co-facilitate. Peer leaders will receive an additional \$60.00 at the completion of the end of the 8th supervision session. This makes the total compensation for the peer leaders co-facilitating a group \$180.00 per group. In addition, peer leaders will also be asked to participate in either an in-person or online (previously recorded) training for the intervention for which you they are co-leading. If attending in person travel expenses (e.g. train, airfare, ground transportation) will be covered by the research award to host them in New Haven, Connecticut. Lodging and per diem expenses will also be covered by the study for up to 3 days. In addition as a token of our appreciation you they will be compensated \$100.00 per day (maximum 3 days) for their attendance in the training.

Participants will be given a choice regarding how they would like to receive payment: either by postal mail or via e-mail. Checks will be mailed to participants, if this is their preferred method. Electronic gift cards will be e-mailed to those who prefer an e-mail delivery.

3. **Costs for Participation (Economic Considerations):** Clearly describe the participant's costs associated with participation in the research, if any, and the interventions or procedures of the study that will be provided at no cost to participants.

Interventions will be at no cost to the participant. A travel stipend will be provided for peer specialists attending various trainings.

References

Aosved, A. C., Long, P. J., & Voller, E. K. (2011). Sexual revictimization and adjustment in college men. *Psychology of Men & Masculinity*, 12(3), 285-296.

Apodaca, T. R., Borsari, B., Jackson, K. M., Magill, M., Longabaugh, R., Mastroleo, N. R., & Barnett, N. P. (2014). Sustain talk predicts poorer outcomes among mandated college student drinkers receiving a brief motivational intervention. *Psychology of Addictive Behaviors*, 28(3), 631-8.

Badgett, M. V. (1995). The wage effects of sexual orientation discrimination. *ILR Review*, 48(4), 726-39.

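### The ID key is to be destroyed when the intervention ends, before the day-60 and day-120 suicide-risk flags that may need it to be traced

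*Combined protocol and SAP*

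**What the plan says.** **The key.** Section V.9 (monitoring plan) and Section VII.3 (Data and Safety Monitoring Plan, item 2) carry the same sentence. Data are coded by a unique ID number, and the document holding the decoding key is destroyed as soon as the intervention is over.

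**The assessments that come later.** Section IV.3 counts the 60- and 120-day follow-ups from the end of the intervention. On suicidality it says: "The C-SSRS screener will be administered during the phone screening interview and at baseline, post-intervention and follow-up assessments". Participants with high-risk answers are flagged, and named study doctors "will conduct a follow-up phone assessment to determine their suicide risk and make a final eligibility determination".

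**Where identities are held.** Section VI.1 keeps personal identifiers separate from the web survey responses. Sections VI.1, VI.5 and VII.2 keep all identifying information for five years. Section VI.7, which asks directly about identifiable data or the link to identifiers, answers that identifiable data go at the earliest date regulations allow.

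**Contact outside sessions.** Under Section V.5, men in the groups are "offered the opportunity to share their e-mail address with their fellow group participants and the two peer leaders for their group". After session 6, they complete a form "to choose if they would like to share their e-mail address with fellow group members and/or peer leaders". The leaders' stated duty in Section VII.2 is to alert the PI "within 30 minutes of the conclusion of the session when the participant expressed, or the peer specialist identified, emotional distress".

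**The concern.** A flagged C-SSRS answer is useful only if someone can telephone the man who gave it. If survey responses are coded and kept apart from names, the key is what turns a flagged record into a person. A rule that destroys the key before the last two C-SSRS assessments takes away the means of acting on them.

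The population makes this matter. Every man enters with a CES-D score of 16 or more. The exclusion is for active suicidality, which Section VII.2 describes as imminent intent with a plan, so men with lesser ideation can be enrolled. The sponsor rates the study as more than minimal risk and makes a suicide attempt immediately reportable. What is at stake is participant safety and the completeness of safety reporting.

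**Working it through.** The plan states no figure on this point, so the check is one of sequence and consistency.

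**Step 1. Order of events, reading the intervention as each man's own group.** Set the end of his six-week group at day 0. The key goes at day 0. The two later C-SSRS assessments fall at days 60 and 120, so 2 of 2 come after the key is gone, for all 356 men. This matches Section IV.3, which starts the follow-up clock at the end of the intervention.

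**Step 2. Order of events, reading the intervention as the whole trial.** Let the last group end at time T, when the key goes. A cycle that ended L days earlier has its follow-ups at T + (60 − L) and T + (120 − L). An assessment is affected when the bracket is positive.

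Section IV.3 anticipates that "new groups will begin every other month (allowing for a two week break between groups"). Six weeks plus two weeks is 8 × 7 = 56 days. Every other month is about 365/6 = 61 days.

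| Cycle length | Cycle | L | 60 − L | 120 − L | Assessments after the key is gone |
|---|---|---|---|---|---|
| 56 | last | 0 | 60 | 120 | both |
| 56 | one before | 56 | 4 | 64 | both |
| 56 | two before | 112 | −52 | 8 | day 120 only |
| 56 | three before | 168 | −108 | −48 | none |
| 61 | last | 0 | 60 | 120 | both |
| 61 | one before | 61 | −1 | 59 | day 120 only |
| 61 | two before | 122 | −62 | −2 | none |

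Three cycles are affected at 56 days and two at 61. Some margins are only a day or two and no assessment windows are given, so the answer is about two to three cycles. The number of groups run in parallel per cycle is not stated, so this cannot be turned into a number of men.

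**Step 3. Can a flag be traced without the key?** Contact details survive for five years. A list of names and telephone numbers does not identify the author of a coded survey unless the list also carries the study ID, and the text does not say that it does. If it does, the link survives elsewhere and destroying the key does not achieve the protection it is offered for. If it does not, the flag cannot be traced. The text needs correcting in either case.

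**Step 4. What else assumes a live link?** Section VIII.2 pays men for each completed assessment, which requires knowing who completed it. The Analysis Plan models repeated observations nested within participants, which requires each follow-up to be tied to the right record. Neither fits easily with a key destroyed before follow-up.

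**The case against.** The strongest reply is that this is one loose sentence, used twice, in a document that elsewhere plainly assumes men stay identifiable: five-year retention, a regulation-based destruction date, payment per assessment and within-person analysis. The sentence also speaks of a single document, and a study-wide key could hardly be destroyed after each closed group, so the trial-wide reading is at least as natural. Much of this stands. It makes a drafting slip likely and means that all 356 men is an upper limit. It does not make the sentence harmless, because the other sections contradict it without overriding it.

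A second reply is that the phone call belongs to screening: its wording ends with an eligibility determination, and Section VII.2 describes the call for the screening interview. But the C-SSRS paragraphs in Section IV.3 list every assessment and then apply the call to any participant who is flagged.

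A third is that the Analysis Plan is in the past tense, so the change may come too late to protect anyone. That limits its prospective value; the contradiction remains.

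A reader might go further and infer that, once e-mail addresses are shared, suicidality disclosed to a leader has no route to help. The documents do not support that:

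- Only the man's address is described as shared, so contact depends on opt-in and on the leader writing first or giving an address.
- Section VII.2 provides resources and emergency advice to anyone reporting ideation during the study, whether or not in a session.
- Section VII.1 gives men who wish to talk further the numbers of study staff and a hotline.
- A psychological safety monitor looks for patterns of adverse events.
- The attestation and sharing forms are attachments that are not in the public text, so silence here is not evidence of a gap.

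**Conclusion.** The key-destruction rule in Sections V.9 and VII.3 is wrong as written. Followed literally, it removes the link between study ID and man before follow-up C-SSRS flags that Section IV.3 requires someone to telephone about, and it conflicts with Sections VI.1, VI.5, VI.7, VII.2 and VIII.2 and the Analysis Plan. Its reach is every participant on the per-man reading and about the last two to three cycles on the trial-wide reading. This assumes that the key is the link between ID and identity and that the retained contact file does not itself carry IDs.

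Two further inferences should be resisted. One is a count of days without supervision after a man's group ends. Leaders receive a payment "at the completion of the end of the 8th supervision session", but that is a payment milestone, and Section VII.2 calls supervision ongoing with no end date. The other is that the treatment comparison is compromised. Nothing here biases the intent-to-treat comparison, and the Analysis Plan describes within-person analyses as already done.

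Whether leaders must report suicidality disclosed outside sessions is a question to confirm with the sponsor and does not affect this conclusion.

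**What to change.** In Sections V.9 and VII.3, change the trigger for destroying the key from the end of the intervention to the close of the last 120-day assessment and its safety follow-up. Align Sections VI.1, VI.5 and VI.7 so that one retention rule covers both the key and the contact file. If follow-up has already closed, record when the key was in fact destroyed and whether every follow-up flag could be acted on.

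The cost is one phrase in two places, a consistency edit and an IRB amendment. The key is held longer, so it needs the same locked storage as the other identifiers. Sample size and analysis do not change.

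As a minor addition, confirm that the peer-leader attestation form covers alerting the PI to suicidality disclosed to a leader outside a session. If it does, a sentence in Section VII.2 repeating it is enough. The e-mail sharing offer can stay as it is.
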